Likely contributors to above measures: Lipid/glucose markers:(fasting C-peptide and lipid panel, HbA1c); hepatic markers:(c-reactive protein, glucagon, GLP-1 and leptin at baseline, 5 min and 30 min post glucose load to asses change with OG, adiponectin, AST, ALT, GGT), sex-steroids:(DHEAS, free and total testosterone, sex hormone binding globulin, progesterone, estradiol); Body size and composition: (BMI, waist/hip ratio, DEXA, hepatic visceral fat via MRI³⁶⁻³⁹), Whole body fat oxidation at rest and following glucose ingestion as measured with a metabolic cart; Physical activity/ diet:(accelerometer, activity survey (3DPAR); Food frequency survey).Questionnaires for presence of obstructive sleep apnea. Questionnaires for perceived mental strengths and difficulty (note there is no assessment of suicidality on this tool). Obstructive Sleep Apnea, to be assessed with an overnight sleep study via WatchPAT.

B. Description of Population to be Enrolled:

Study staff aims to enroll 20 obese girls with regular menstrual cycles, 20 girls with un-treated PCOS, 20 girls with PCOS treated with at least 6 months of Metformin and 20 girls with PCOS treated with at least 6 months of oral contraceptives. The PCOS groups will be compared to 20 obese non-PCOS controls. This is the number of participants needed to be completed statistically, thus more subjects may be enrolled, to allow for screen failures and dropouts. Total enrollment will be up to 100 participants.

Ethnic Categories	Gender		
	Females	Males	Total
Hispanic or Latino	40	0	40
Not Hispanic or Latino	60	0	60
Ethnic Categories: Total of All Subjects	100	0	100
Racial Categories			
American Indian/Alaska Native	5	0	5
Asian	10	0	10

Native Hawaiian or Other Pacific Islander	10	0	10
Black or African American	32	0	32
White	43	0	43
Racial Categories: Total of All Subjects*	100	0	100

Inclusion Criteria:

- 1) Female
- 2) Ages 12-21
- 3) Sedentary- less than 2.5 hours of moderate (jogging, swimming etc) exercise a week.
- 4) BMI equal or greater than the 90th percentile for age and gender
- 5) For PCOS groups: (NIH definition) irregular menstrual cycles at least 1.5 years after menarche and either clinical evidence of hyperandrogenism or elevated Testosterone (above the norms for age/tanner stage) at time of screening or documented prior to initiation of therapy for OCP and metformin groups.

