- 6) For PCOS groups: patients un-treated or currently treated with either Metformin 1500-2000 mg a day or oral contraception (30-35 mcg ethynodiol a day) for at least 6 months, with > 80% adherence confirmed via refill frequency from pharmacy.
- 7) For non-PCOS groups: regular menstrual cycles at least 1.5 years after menarche and no clinical evidence of hyperandrogenism

Exclusion Criteria:

1. Use of medications known to affect insulin sensitivity: oral glucocorticoids within 10 days, atypical antipsychotics, immunosuppressant agents, HIV medications. Nexplanon, Depo-Provera or Mirena progesterone only contraceptives. Dermal patch or vaginal ring contraception methods. For controls only: metformin or oral contraception.
2. Currently pregnant or breastfeeding women. Development of pregnancy during the study period will necessitate withdrawal from the study.
3. Severe illness requiring hospitalization within 60 days
4. Diabetes, defined as Hemoglobin A1C > 6.4%
5. BMI percentile less than the 90th percentile for age and sex. Weight >325 lbs or <84 lbs.
6. Anemia, defined as Hemoglobin < 10 mg/dL
7. Diagnosed major psychiatric or developmental disorder limiting informed consent
8. Implanted metal devices that are not compatible with MRI
9. Use of blood pressure medications
10. Known liver disease other than NAFLD or AST or ALT >150 mg/mL

Rationale for Inclusion of Non-PCOS Subjects

Obese adolescents are at risk of T2D and its complications, reduced exercise capacity, increased liver and visceral fat, muscle dysfunction and cardiovascular dysfunction therefore the tests

performed screening for each of these problems provide useful information to these subjects. Likewise, sedentary subjects of any weight are at increased risk of reduced bone mineral density (BMD), T2D, reduced exercise capacity, increased liver and visceral fat, muscle dysfunction and cardiovascular dysfunction. Therefore, all of the subjects may benefit from the results of DEXA, glucose testing and exercise prescription and dietary counseling.

C. Study Design and Research Methods

Study Calendar	Visit 1 – Screen	Visit 2 –MRI	Visit 3 – Overnight
Consenting and Eligibility Assessment	X		
History & Physical	X		
Intravenous Blood Draw	X		X
Finger Stick Blood Draw		X	
Urine Pregnancy Test			X
Accelerometer Teaching	X		
Gut Bacteria Collection			X
Questionnaires- SEARCH Food frequency, Activity 3DPAR, Strengths and Difficulties and Sleep assessments			X

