Since the recommendations are not concrete for the 12-17 year old range, we sought to follow what is being done in clinical practice at Children's Hospital Colorado sleep clinics, were a patient to have an inpatient polysomnogram. Sleep studies are read within 5 business days, and we will adhere to this same turnaround timeline. In terms of interpretation, currently, the pediatric guidelines are being applied for the 12-17 year old age group but 2 is considered normal in this age, and thus our post-study for the 12-17 year olds will follow this, and are shown below. Approximately half of the participants have a patient relationship with the PI [name], and thus she can order F/U evaluation if needed, and if not, [name] will request the follow-up be arranged by the primary care provider. We have 2 algorithms by age.

For participants 12-17 years of age:

For participants ≥ 18 years of age:

SUBJECT RECRUITMENT/CONSENT/PAYMENT

1. Subject Recruitment Plan

Subjects will be recruited from pediatric endocrine, PCOS, Lifestyle, adolescent and gynecology clinics, and from the community. We receive 4-8 new PCOS referrals a month, showing the feasibility of recruiting the required subjects. Further, we enrolled >100 obese girls in studies in the last 60 months. The PI and Co-I's have a treatment relationship with girls from clinic or subjects

can call from study advertisements. Protected health information will only be accessible by study investigators. The initial patient contact will be made by personnel who have a treatment relationship with the subject. Our past studies have consented participants and asked if they'd like to be re-contacted for future research studies. Furthermore, after the conclusion of our previous studies in PCOS (this protocol, 14-0542 and 10-1288), participants may have been prescribed treatment with OCP or Metformin, therefore study staff may aim to re-contact them had those participants agreed to be re-contacted and still meet inclusion criteria of the current study.

2. Informed Consent Plan

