Power calculation: The primary outcome is hepatic substrate flux pathway percentages measured as PEP, TCA and TG synthesis pathways. Power analysis is based on publications utilizing similar methods, with the Primary Aim of understanding differences in hepatic metabolism in obese girls with PCOS who either have or do not have hepatic steatosis. The reference manuscript included 13 men without HS, and 6 men with HS⁵⁰. They found that during hyper-insulinemia, glycerol related gluconeogenesis was increased, as was the PEP cycle in individuals with HS compared to those without. Utilizing the PEP value, from this paper, the difference between the group means is 3 μ mol.min.kg FFM, and the standard deviation is 2 μ mol.min.kg FFM. Differences between the two primary groups (PCOS, controls) will be assessed with a t test or for non-normally distributed data a non-parametric test such as Mann-Whitney U. With 15 untreated PCOS with HS and 15 untreated PCOS without HS, we would have a power of 0.97 to detect an alpha of 0.05. Since the reference population is men who have more uniform hormone profiles, I am choosing to be overpowered should the variability in our population be greater. As the measurement is in kg of fat free mass, we will not have to do adjustments with BMI or weight. However, as African Americans are less likely to have HS, and Hispanics more likely to have HS, if ethnicity percentages are different between groups, we will need to adjust for ethnicity in our calculations.

Secondary Aims: a) For comparison of the PCOS to control groups, individuals will be matched in terms of HS status, so that the comparison is just between the hormonal state. I am assuming that there will be less of a difference between these groups, so with a difference of 2 Umol.min.kg FFM, and the standard deviation is 2, with 20 PCOS and 20 controls, we would have a power of 0.87 to detect a alpha of 0.05. b) For comparison of treatment with either metformin or OCP's, we will compare the untreated group to the treatments individually. We will not compare the two treatments to each other. I am assuming that there will be less of a difference between these groups, so with a difference of 2 Umol.min.kg FFM, and the standard deviation is 2, with 30 PCOS and 15 in a treatment group, we would have a power of 0.87 to detect a alpha of 0.05.

All measures will be adjusted for OSA status (yes/no) and/or severity of AHI.

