Secondary outcomes include a Pearson correlation test of potentially related variables followed by targeted multiple regression to assess the relationship between hepatic fat and adipose IR, PEP, TCA, TG synthesis pathways.

Non-Isotope OGTT calculations: The Matsuda model of IR will be used but adapted for the 6.5 hour OGTT, and B-cell function [insulinogenic index ($\Delta I30/\Delta G30$) and ($\Delta C30/\Delta G30$) and disposition index ($1/I_{Fasting} \times \Delta I30/\Delta G30$) and ($1/C_{Fasting} \times \Delta C30/\Delta G30$) will be calculated^{38,49,51,52}.

Differences between groups will be evaluated with and without controlling for activity and sleep status.

Fitting glucose and glycerol concentrations curves: Using computed data points, glycerol and glucose concentrations will be fitted with an appropriate model. In control subjects, concentration typically shows 3 phases in OGTT ⁵³. Cubic polynomial, piecewise-linear, spline, and dynamic models have been used for fitting Ra in previous work^{54,55}. We will assume a cubic polynomial model; we will validate estimates obtained with the cubic polynomial model by computing comparable estimates using at least one other model form. In previous work comparing different models (piecewise-linear, cubic polynomial, dynamic), results have been relatively unaffected by choice of model. If we find that this is not the case for our data, then we would certainly consider the advantages of adopting a more complex approach, such as the state-space, for describing concentration changes.

Metabolomics data: Differences in targeted metabolic concentrations will be compared between groups, after appropriate cleaning of the data, as performed by the processing site. Changes in metabolites over time will be compared between groups, to determine the times that demonstrate the largest differences. Results will also be compared to isotopomer results, to see if a metabolomics endpoint can yield similar information to the isotopomer analysis.

Gut Microbiota: The microbiota profile is entirely exploratory, and will be related to status of hepatic steatosis and 2 hour glucose status of impaired glucose tolerance or not.

VIII. Summarize Knowledge to be Gained:

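### Non-randomised groups aged 12 to 21 are compared with a named adjustment set that leaves out age and time since menarche, so age differences may be mixed with treatment, PCOS or steatosis effects.

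*Combined protocol and SAP*

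**What the plan says.** Section III.B sets four groups: obese controls, untreated PCOS, PCOS on metformin and PCOS on oral contraceptives. Membership follows diagnosis and existing treatment; nothing is randomised. The age range is 12 to 21 in every group, with no age stratum, quota or matching.

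The entry rules that bear on time since menarche are:
- PCOS groups (criterion 5): "irregular menstrual cycles at least 1.5 years after menarche", plus hyperandrogenism "at time of screening or documented prior to initiation of therapy for OCP and metformin groups".
- Treated PCOS groups (criterion 6): treatment "for at least 6 months, with > 80% adherence confirmed via refill frequency from pharmacy".
- Controls (criterion 7): "regular menstrual cycles at least 1.5 years after menarche and no clinical evidence of hyperandrogenism".

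The Subject Recruitment Plan adds that, after the group's PCOS studies, "participants may have been prescribed treatment with OCP or Metformin", and that such girls may be re-contacted for this study.

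Section VII sets out how the groups will be compared. It states "All measures will be adjusted for OSA status (yes/no) and/or severity of AHI". It also says that "if ethnicity percentages are different between groups, we will need to adjust for ethnicity in our calculations". After the non-isotope OGTT calculations it adds "Differences between groups will be evaluated with and without controlling for activity and sleep status". BMI and weight are judged unnecessary because flux is expressed per kg of fat-free mass. PCOS and control girls are matched on HS status. Neither age, Tanner stage nor time since menarche appears as a covariate or matching factor, and none is among the likely contributors in Section III.A.

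**The concern.** In an observational comparison, any factor that differs between groups and is related to the outcome can pass for a group effect. Age is an obvious candidate in a sample running from 12 to 21. The protocol itself treats age and hormonal state as relevant: testosterone is judged against norms for age and Tanner stage, and estradiol is listed as affecting insulin resistance and hepatic lipogenesis. Yet a plan that always adjusts for sleep apnoea, and conditionally for ethnicity, gives no reason for omitting age.

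For treated v untreated PCOS (secondary aim b) there is a further reason to expect a gap. A treated girl must meet the PCOS definition and have at least six months of treatment behind her. Re-contacting former participants who have since started treatment could push the same way. If flux varies with age, the unadjusted contrast would be biased, in either direction, and its error rate would not be the nominal one.

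**Working it through.** **1. The plan's own power figures.** Two-sided two-sample t test, alpha 0.05, noncentral t, SD 2 (Section VII):

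| Comparison | n | Difference | Stated | Recomputed |
|---|---|---|---|---|
| HS v no HS, untreated PCOS | 15 v 15 | 3 | 0.97 | 0.977 |
| PCOS v control (secondary a) | 20 v 20 | 2 | 0.87 | 0.869 |
| Untreated v treated (secondary b) | 30 v 15 | 2 | 0.87 | 0.871 |

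The figures reproduce, so the same test is used below.

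**2. What the entry rules fix.** Untreated PCOS and controls: minimum 1.5 years after menarche. Treated PCOS: 1.5 + 0.5 = 2.0 years, if the irregular cycles came before therapy. This moves a minimum, not a mean. If time since menarche is uniform up to a common limit U, the means differ by (2.0 + U)/2 − (1.5 + U)/2 = 0.25 years. If it has an exponential tail above the minimum, they differ by 0.5 years. With the same age at menarche in all groups (assumed), these are also the age gaps.

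HS v no HS within untreated PCOS, and untreated PCOS v control, share the 1.5-year minimum, so no gap is built in there.

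**3. Bias.** The documents give no group ages, age SD or age slope. Assumed: age SD 2.5 years; within-group correlation r between age and flux of 0.2 to 0.4. The outcome SD of 2 is the plan's.

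Bias = r × (2 / 2.5) × gap. Its share of the planned effect is bias / 2. The false-positive rate is the rejection probability of the unadjusted t test when the true difference is zero and the means differ by the bias. The standard error is 2 × √(1/20 + 1/20) = 0.632 for 20 v 20, and 2 × √(1/30 + 1/15) = 0.632 for 30 v 15, so the two designs give nearly identical rates.

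| Mean age gap | r | Bias | Share of 2 | False positives |
|---|---|---|---|---|
| 0.25 y | 0.2 | 0.04 | 2% | 5.04% |
| 0.5 y | 0.4 | 0.16 | 8% | 5.7% |
| 1 y | 0.2 | 0.16 | 8% | 5.7% |
| 1.5 y | 0.3 | 0.36 | 18% | 8.6% |
| 2 y | 0.4 | 0.64 | 32% | 16.7% |

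The first two rows bracket the entry-rule shift alone. The last three need a gap that the rules allow but do not produce.

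**4. Cost of adjusting.** Adding age inflates the variance of the group contrast by 1 + [n1·n2/(n1 + n2)] × gap² / [(N − 2) × SD_age²] and multiplies the residual variance by 1 − r². For 20 v 20, a 2-year gap and age SD 1.5, the inflation is 1 + 10 × 4 / (38 × 2.25) = 1.468, and power at r = 0 is 0.72. Over age SD 1.5 to 2.5 and r 0 to 0.4, power is about 0.83 to 0.91 at a 1-year gap and 0.72 to 0.88 at 2 years, against 0.87 planned.

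**The case against.** A reader might infer that the entry rules make treated girls later after menarche than untreated girls and controls, so that age and puberty effects will be reported as treatment effects. The documents do not support that:

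- The rules set minimums only. An untreated girl or a control may be many years past menarche, up to age 21.
- Even the half-year shift depends on how criterion 5 is read. The wording about documentation before therapy sits beside the hyperandrogenism item and does not plainly govern the irregular cycles.
- The shift concerns only comparisons involving a treated group. The primary powered contrast lies within untreated girls.
- Every participant is at least 1.5 years past menarche, which narrows the pubertal spread, and scaling by fat-free mass already deals with part of body composition. No age-flux relation is given anywhere, so the correlations used here are assumptions.
- Adjustment costs more than a degree of freedom when age and group are correlated, and age would join several other covariates in groups as small as 15.

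All of this stands, and it limits the size and certainty of the bias. It does not remove the omission. HS matching, fat-free-mass scaling and the named covariates do not balance age, and without randomisation nothing else in the plan does.

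**Conclusion.** The concern holds as a gap in pre-specification: Section VII names its covariates, and age and time since menarche are not among them. The resulting bias is possible, not demonstrated. From the entry rules alone it is small, and it applies only to comparisons with treated girls: 0.04 to 0.16 units and at most 5.7% false positives under the assumptions above. It becomes material, up to 0.64 units and 16.7%, only if mean ages differ by 1 to 2 years, which selection or re-contact could bring about but which no rule requires. For untreated PCOS v control and for HS v no HS the issue is ordinary age confounding with no built-in gap. All sizes rest on the assumed age SD and correlations. The change should be made before outcome data are examined.

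**What to change.** In the statistical plan of Section VII, beside the OSA adjustment, pre-specify age in years as a covariate in the between-group models for primary and secondary outcomes. The t test and Mann-Whitney test named there cannot carry a covariate, so age belongs in the regression model that the OSA adjustment already needs. Report age and time since menarche by group. As a sensitivity analysis, replace age by time since menarche.

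Age needs no new data: date of birth is among the items collected under Section VI. Eligibility already turns on time since menarche, so age at menarche need only be recorded as a value.

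The cost is one degree of freedom, plus some precision if ages differ by group. At a gap of about a year the loss is small, and power can rise if age predicts flux. At 2 years power could fall to 0.72 in the worst case considered; in that case the unadjusted estimate would be the less trustworthy one if age is related to flux.

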Title: Post-Prandial Liver Glucose Metabolism in Polycystic Ovarian Syndrome (PCOS) and understanding Standard of Care Medications

Version Date: 8/17/2017

NCT03041129

COMIRB Protocol

COLORADO MULTIPLE INSTITUTIONAL REVIEW BOARD
[name] [contact] [contact]

Project Title: Post-Prandial Liver Glucose Metabolism in Polycystic Ovarian Syndrome (PCOS) and understanding Standard of Care Medications

Version Date: 8/17/2017

Principal Investigator: [name] [name], PhD

I. Hypotheses and Specific Aims:

HYPOTHESIS:

Obese girls with hepatic steatosis (HS) will have hepatic glucose metabolism that is upregulated towards de novo lipogenesis (DNL) via multiple intrahepatic pathways, compared to PCOS without HS and obese controls without HS. HS will be related to relative post-prandial hyperglycemia. Post-prandial hyperglycemia will be made worse or remain unchanged with oral contraceptives and better with metformin.

Specific Aims:

Aim 1: In obese girls with PCOS, post-prandial hepatic substrate metabolism will differ by HS status and treatment regimen and can be assessed with just an oral tracer protocol combined with NMR isotopomer analysis.

Hypothesis: Girls with HS will have upregulated post-prandial hepatic non-glycogenic metabolism compared to those without HS. This will be unchanged by oral contraceptives, and decreased with metformin.

Rationale: A marker of whole body DNL was increased in girls with HS, and preliminary work from my K23 project indicates that direct measures of DNL are elevated, but upstream alterations in intrahepatic metabolism are unclear. Oral contraceptives do not mitigate metabolic risk, whereas metformin decreases HS.

Methods: A 6.5 hour OGTT with an oral U-C₁₃glycerol tracer will be paired with NMR isotopomer analysis of serum samples to describe flux through the hepatic pentose phosphate pathway, TCA cycle and DNL pathways in girls with PCOS receiving lifestyle only, metformin or oral contraceptive treatment, and obese girls with regular menses receiving lifestyle therapy.

Aim 2: Describe the optimal timing for identifying metabolomics profiles associated with risk for T2D and HS.

Hypothesis: Metabolomics profiles between girls with HS and worse IR will differ the most between 3-6 hours.

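### The hepatic fat–pathway correlations name no analysis population and no group term, so a metformin effect on both variables could pass for an association between them

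*Combined protocol and SAP*

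**What the plan says.** Section VII describes the method in one sentence: "Secondary outcomes include a Pearson correlation test of potentially related variables followed by targeted multiple regression". Its stated purpose is "to assess the relationship between hepatic fat and adipose IR, PEP, TCA, TG synthesis pathways". No analysis population, covariate list, group term or rule for moving from correlation to regression is given.

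Elsewhere in Section VII, adjustment for sleep apnoea status or AHI is promised for all measures. Ethnicity is to be adjusted for only if it is unbalanced between groups. Activity and sleep are named for the group comparisons. Group or treatment is not named as a covariate anywhere.

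Section III.B sets out the sample: "20 girls with un-treated PCOS, 20 girls with PCOS treated with at least 6 months of Metformin", a further 20 on oral contraceptives, and "The PCOS groups will be compared to 20 obese non-PCOS controls".

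Section I, Aim 1, states what treatment is expected to do. On steatosis: "Oral contraceptives do not mitigate metabolic risk, whereas metformin decreases HS". On non-glycogenic hepatic metabolism: "This will be unchanged by oral contraceptives, and decreased with metformin".

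**The concern.** The sample is assembled by PCOS status and treatment, not drawn as one population. On the plan's own premises metformin lowers both variables being correlated. When groups with different means on both variables are pooled, the difference in means produces a correlation even if the two are unrelated within every group. A Pearson coefficient cannot carry a group term, so the first step is exposed whenever groups are pooled. The regression is exposed too if its only covariate is the sleep apnoea term already promised.

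At stake is the interpretation. These analyses are meant to show how liver fat relates to the pathways, and Section VIII expects the study to supply background evidence for later therapeutic trials. A treatment difference read as a metabolic link would carry forward into that work. The primary comparison by steatosis status is not affected.

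**Working it through.** **1. The plan's figure for the pathway difference.** Section VII powers the treatment comparison on a difference of 2, and "the standard deviation is 2, with 30 PCOS and 15 in a treatment group", stating power 0.87. The noncentrality is 2 / (2 × √(1/30 + 1/15)) = 3.16 on 43 degrees of freedom; a two-sided t test at 0.05 then has power 0.871. The PCOS–control comparison (20 and 20, same difference and SD) gives noncentrality 3.16 on 38 degrees of freedom and power 0.869, against 0.87 stated. Both reproduce. The planned pathway shift is therefore 2/2 = 1 SD. The documents give no power or sample size for the correlations.

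**2. Inputs.**
- Four groups of 20, N = 80 (Section III.B).
- Pathway lower by 1 SD in the metformin group (size from Section VII, direction from Aim 1).
- Hepatic fat lower by d SD in the metformin group. The documents give no size, so d is an assumption, taken from 0 to 1.
- Correlation of zero within every group, within-group SD of 1 on each scale.

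**3. Only metformin differs.** One quarter of the sample is shifted.
- Covariance created by pooling: (1/4)(3/4) × d × 1 = 0.1875d
- Pathway variance: 1 + 0.1875 = 1.1875
- Fat variance: 1 + 0.1875d²
- Pooled r = 0.1875d / √[1.1875 × (1 + 0.1875d²)]

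For d = 1, r = 0.1875/1.1875 = 0.158. By Fisher's transformation z = √77 × atanh(0.158) = 1.40, and the two-sided rejection rate is Φ(1.40 − 1.96) + Φ(−1.40 − 1.96) ≈ 0.29.

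**4. Controls also lower on the pathway by 1 SD, but equal on fat.**
- Covariance: d/4 − (d/4)(1/2) = 0.125d
- Pathway variance: 1 + (1/2)(1/2) = 1.25
- Pooled r = 0.125d / √[1.25 × (1 + 0.1875d²)]

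For d = 1, r = 0.103, z = 0.90, and the rejection rate is about 0.15.

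**5. Check by simulation.** Several thousand simulated studies per row, with Monte Carlo error below 0.01, agree with the formula to about 0.01:

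| Fat shift d (SD) | r, metformin only | False-positive rate, metformin only | r, controls differ on pathway only | False-positive rate, controls differ on pathway only |
|---|---|---|---|---|
| 0 | 0.00 | 0.05 | 0.00 | 0.05 |
| 0.25 | 0.04 | 0.06 | 0.03 | 0.06 |
| 0.5 | 0.08 | 0.11 | 0.05 | 0.08 |
| 0.75 | 0.12 | 0.20 | 0.08 | 0.11 |
| 1 | 0.16 | 0.29 | 0.10 | 0.14 |

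The r columns come from the formulas, the rates from simulation. With three group indicators in the model, the rate is about 0.05 throughout.

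**The case against.** The strongest reply is that the defect is read from silence. The documents never say the four groups are pooled, and a multiple regression whose terms are not listed could include group. That is correct, and it limits the claim to what the text permits. It does not remove the problem. The Pearson step cannot include group, and the choice between pooling and stratifying would be made with the data in view.

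A second reply is that a group term may remove real signal, since metformin might lower fat through these very pathways. That is possible, but a pooled correlation cannot separate that mechanism from two unrelated effects of treatment. Reporting within-group results keeps the question visible.

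Four stronger readings are tempting, and the documents do not support them.
- *A false link will be reported.* Even in the worst row above, about 71% of studies would show none. The 1 SD figure is the plan's for the pathway only; its use for fat is an assumption.
- *The rate reaches 44%.* That needs a second group lower by 1 SD on both variables. Aim 1 expects oral contraceptives to leave the pathways unchanged, and Section VII matches controls to PCOS participants on steatosis status for that comparison.
- *Screening some 35 contributors makes a chance finding nearly certain.* Section III.A does list many contributors, for example "sex-steroids:(DHEAS, free and total testosterone, sex hormone binding globulin, progesterone, estradiol", but the plan calls the regression targeted, names its subject and gives no p-value screen over that list. For four unrelated predictors, the chance that at least one passes 0.05 is 1 − 0.95⁴ = 19%.
- *Hepatic fat is clearly skewed.* The pilot value is 10.5±2.6 with N = 13. If ± is a standard error, the SD is 2.6 × √13 = 9.4, which on a non-negative scale implies skew. If it is an SD, there is no such sign. The table does not say which.

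**Conclusion.** The concern holds as a gap with a definite consequence. Followed literally, the stated method has no group term, although the plan itself predicts that one group will be lower on both variables. The false-positive rate of a pooled Pearson test would be about 6% to 29% for an assumed metformin fat shift of 0.25 to 1 SD. It would be about 5% to 14% if controls also differ on the pathway but are matched on fat. If fat does not differ by group, it stays at 5%.

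This rests on pooling all four groups, a 1 SD pathway difference, and zero within-group correlation. The arithmetic concerns the pathways; the documents give no expected treatment effect on adipose insulin resistance, so no rate can be attached to that pair. This is a secondary analysis, but one worth correcting before the data are analysed.

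**What to change.** Replace the pooled Pearson step with pre-listed linear models of hepatic fat, one for each of the three pathways and one for adipose insulin resistance. State the analysis population. Include group (four levels) as a covariate alongside the sleep apnoea term that is already planned. Log-transform hepatic fat, or use a rank-based version, if it proves skewed. Report partial correlations and the within-group correlations, and label correlations with the other listed contributors exploratory.

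The cost is a few lines of plan text and three degrees of freedom: with 80 participants and one predictor, residual degrees of freedom fall from 78 to 75, before the sleep apnoea term. The headline correlation may also be weaker than a pooled one. Group is already recorded, so no new data are needed.
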